that changes in the inflammatory peptide correlated closely with increases in the peak VO_2 (56). An even more interesting relationship was demonstrated by Gielen et al., who showed that exercise induced changes in cytokine expression in humans are relatively greater at the level of the skeletal muscle tissue than they are by serum assays, *providing strong rationale to study effects of exercise on a local tissue level rather than serum level, to ascertain true exercise training effects* (23).

Data showing benefits of exercise training to increase IGF-1 in humans are also relatively sparse. [name] and coworkers completed a seminal study that showed increased local skeletal muscle IGF-1 expression among stable HF patients after 6 months of aerobic exercise training (57). Another study by [name] and his coworkers focused on healthy older adults, exploring the benefits of a combined nutritional supplementation and resistance training regimen on local skeletal muscle IGF-1 expression. After 10 weeks, the investigators showed a 6-fold increase in local IGF-1 expression (58).

A series of recent investigations have focused on exercise benefits to stimulate PGC-1 α . Kuhl et al. showed benefit of a combined aerobic-strength regimen to increase PGC-1 α in healthy adults (59), while a low-intensity endurance regimen in coronary artery patients did not induce similar PGC-1 α changes (60). Other literature reflects similar inconsistencies: Pilegaard et al showed robust PGC-1 α effects after 4 weeks of leg extensor exercise (50), while Konopka et al. showed no similar PGC-1 α responses (52). Furthermore, as part of their study on a knee extension stimulus, Norrbom et al. postulated that the type of exercise may be relevant, with strength training much more likely to stimulate PGC-1 α than aerobic type exercise (61).

Exercise Training: Multiple training modalities, each with physiological rationale

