A randomized controlled IMT trial in HF patients by Laoutaris et al. also showed that increased aerobic effects from IMT (72). IMT led to increased maximal inspiratory pressure (Pimax), (111 ± 6.8 versus $83 \pm 5.7 \text{ cmH}_2\text{O}$, $p < 0.001$), and sustained maximal inspiratory pressure (SMIP) (527822 ± 51358 versus $367360 \pm 41111 \text{ cmH}_2\text{O/sec} \times 10(-1)$, $p < 0.001$), and also increased peak VO_2 (17.8 ± 1.2 versus $15.4 \pm 0.9 \text{ mL O}_2 \cdot \text{kg}^{-1} \cdot \text{min}^{-1}$, $p < 0.005$), and 6MWT distance (433 ± 16 versus 367 ± 22 meters, $p < 0.001$). Moreover, perceived dyspnea, assessed using the Borg scale, was reduced for both on the treadmill (12.7 ± 0.57 versus 14.2 ± 0.48 , $p < 0.005$) and walking (9 ± 0.48 versus 10.5 ± 0.67 , $p < 0.005$) evaluations. Quality of life score was also improved (21.1 ± 3.5 versus 25.2 ± 4 , $p < 0.01$).

There are two commonly used devices for IMT, the threshold IMT and the Test of Incremental Respiratory Endurance (TIRE) IMT. Both devices involve inhaling against a resistance to stimulate diaphragmatic strengthening. Threshold IMT device is the most widely used technique (12,13,73). TIRE IMT provides a

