[name] brings a key expertise as a leader in the field of IMT and will guide this critical component of the study. Working with Drs. [name] and [name], he completed an IMT study on advanced HF patients (NYHA class III and IV, LVEF 23 \pm 13%) and found improvements in maximal inspiratory and expiratory pressures as well as symptoms as early as two weeks after initiating an IMT regimen that was far more convenient and efficient than others which had been studied at that time (73). A subsequent study by Drs. [name], [name], and [name] also examined the effects of IMT in advanced HF patients, but employed a cross-over design and compared IMT to cycle ergometry (CE) (75). The results of that study demonstrated the effects of "specificity of training" with IMT significantly improving inspiratory muscle strength and endurance and CE significantly improving cycling performance. Both IMT and CE significantly improved 6MWT distance, estimated peak VO₂, and quality of life, with IMT eliciting relatively greater improvements (75). [name] and his colleagues also performed a comprehensive review of the effects of diaphragmatic breathing in patients with chronic obstructive pulmonary disease (COPD) (74) and identified similarities in several respiratory indices of HF and COPD patients.

MATERIALS AND METHOD

In a 4-year randomized, controlled trial, the efficacy of 3 exercise training regimens to modify symptoms of exercise intolerance and dyspnea in older systolic HF patients will be compared. Since aerobic training, combined aerobic and strength training, and IMT each constitute different training stimuli, we expect to find differences in how HF patients undergoing each regimen are affected with respect to functional attributes as well as in terms of constitutive skeletal muscle features (phenotype and gene signal patterns). We anticipate insights from this work will facilitate clinical implementation of exercise training that more efficiently yields improvements in highly relevant parameters (improved symptoms and functional capacity) and which also better moderate peripheral pathophysiological aspects of the disease (such as skeletal muscle and tissue perfusion). Patients will be randomized between 4 different exercise training regimens, and endpoints will focus on functional differences, in skeletal muscle phenotypes, gene expression, as well as related differences in skeletal muscle vascular perfusion and serological differences in metabolism and inflammation.

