General considerations: The analyses described below are of continuous outcome measures, primarily changes in function outcomes and gene expression and either continuous or categorical predictors. All analyses will be performed as general linear models. Potential confounders of each analysis will be outlined below and a 10% rule for evaluating confounders will be used, namely including a potential confounder if a 10% or greater change is seen in the main predictor effect. In all instances, outcome variables will be evaluated for violation of regression assumptions and transformation of these variables will be considered as a remedy if needed. Analyses will generally be performed with an intent-to-treat approach, with sensitivity analyses performed to assess the role of drop-outs on the results.

This grant examines a complex interplay of exercise regimens, gene expression and functional measures, resulting in a number of hypotheses that require testing. We are cognizant of the role of type I error in this and in interpreting results, focus will be placed on the overall results of these analyses and not on the results of individual tests. Thus, for example, significant relationships among gene expression outcomes and treatment categories as a whole will be considered as support for these hypotheses and isolated significant associations will not be unduly weighted in the interpretation of results.

Randomization will be generated using a SAS program based upon permuted random blocks of variable size to assure approximate balance over time and will be stratified by sex and statin use.

Validation of Study Measurements: At the start of the study, there will be two assessments of physical function battery. Intraclass correlations will be used to determine the relative repeatability of the various components of the battery. This information will be included in all manuscripts using these measures.

- *Aim 1. To assess differences in functional outcomes (peak VO₂, 1RM) relative to the training therapy:*

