a) *Aerobic vs. Strength vs. Aerobic-Strength regimens will be compared to one another b) Inspiratory Training will be compared to Aerobic-Strength:* In this aim, we compare the combined aerobic-strength training regimen to the single-therapy regimens of aerobic training and strength training, as well as the inspiratory training regimen. These comparisons will be made with changes in the functional outcomes (peak VO₂, 1RM) from baseline as the continuous outcome measures in separate models and training regimen as the categorical predictor in a general linear model, with the following factors considered as potential confounder variables: age, sex, and comorbidities. To limit the type I error rate, only the pre-planned comparisons of the combined aerobic-strength training to the other regimens will be considered. In addition, secondary analyses will consider the following aerobic, strength and inspiratory variables as outcome variables in similar analyses to those outlined above: 6MWT, sit-to-stand, and hand grip strength.

- **Aim 2. To assess gene expression and skeletal muscle perfusion in relation to the different training regimens:** In this aim, we examine the change from baseline to post-exercise regimen in the expression of proteolytic (FoxO and Ubiquitin) and anti-proteolysis (IGF-1 and PGC-1 α) genes as predictors of the change in functional outcomes (peak VO₂, 1RM) over the same period. Separate general linear models for each functional outcome will be performed with gene expression changes as the primary predictor and the following variables considered as potential confounders: age, sex, and comorbidities. As above, a 10% rule for introducing confounding variables and the transformation of outcome variables to deal with regression assumption violations will be considered.

Treatment regimens will also be categorized as those with and without direct skeletal muscle stimulation and this categorical variable will be considered as a predictor of a change in the expression of proteolytic and anti-proteolysis genes in general linear models in a similar fashion to that described above. In addition, similar general linear models will be used with changes in skeletal muscle perfusion as a continuous outcome and aerobic and inspiratory training vs. strength-only training as a categorical predictor with similar potential confounders as noted above.

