Secondary analyses will include assessment of the relative impact of changes in skeletal gene expression vs. changes in perfusion dynamics as predictors of changes in function and quality of life as outcomes. Measures of changes from baseline in serum inflammation, cytokines, and adipokines, and effects of muscle histology will be included as covariates in these analyses. General linear models will be used (outlined above).

Sample size/Power: In this study, we plan to recruit 210 individuals and assign them to one of 4 treatment arms, i.e., randomized between aerobic, aerobic strength, and IMT in VAPHS and between aerobic and inspiratory muscle training in Boston. Sample size calculations are based on 20% attrition over the course of the study. In general, a sample size of 40 per group, using a t-test of independent samples as a simplified model, results in an effect size of 0.64 SD units for 80% power, using a two-sided alpha of 5%.

- **Aim 1:** For this aim, we present calculations for detecting differences in peak VO₂. Previous work by Becker (108) shows a $2.1 \text{ mL O}_2 \cdot \text{kg}^{-1} \cdot \text{min}^{-1}$ change in peak VO₂ in a 6 month aerobic-strength training regimen. Similarly, Tyne-Lenne, et al. shows a $1.1 \text{ mL O}_2 \cdot \text{kg}^{-1} \cdot \text{min}^{-1}$ change in a strength-only regimen (109), HF-ACTION (85) shows a $0.6 \text{ mL O}_2 \cdot \text{kg}^{-1} \cdot \text{min}^{-1}$ change in an aerobic regimen and the IMT trial by Dall'Ago et al. (12) shows a $4 \text{ mL O}_2 \cdot \text{kg}^{-1} \cdot \text{min}^{-1}$ change with inspiratory training. Standard deviations [SD] of the change in peak VO₂ over an exercise regimen are not directly available but using interquartile range values from the largest study [HF-ACTION, n=1442], we obtain a SD value of 2.2 for a 3-month intervention. This would correspond to detecting a difference of $1.26 \text{ mL O}_2 \cdot \text{kg}^{-1} \cdot \text{min}^{-1}$ in any comparison with 80% power, assuming a SD=2.2.

- **Aim 2:** In a similar fashion, a simplified comparison of those with gene expression below the median vs. those above the median would be able to detect a difference of $1.26 \text{ mL O}_2 \cdot \text{kg}^{-1} \cdot \text{min}^{-1}$ in peak VO₂ with 80% power. Analyses of combined training groups facilitates capacity to detect smaller differences between groups.

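### Aim 2's gene-to-function model leaves out training regimen, so its slope can mix differences between regimens with the link within a regimen

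*Combined protocol and SAP*

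**What the plan says.** The statistics text for Aim 2 fits separate general linear models for change in peak VO2 and change in 1RM, "with gene expression changes as the primary predictor and the following variables considered as potential confounders: age, sex, and comorbidities". General considerations sets the entry rule: "Potential confounders of each analysis will be outlined below and a 10% rule for evaluating confounders will be used". A variable not outlined for an analysis is therefore never put to the 10% test.

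Regimen does appear in other models. It predicts function in Aim 1. In grouped form it predicts gene change and perfusion in the second paragraph of Aim 2: "Treatment regimens will also be categorized as those with and without direct skeletal muscle stimulation". The secondary models that relate gene and perfusion changes to function add serum markers and histology, but not regimen.

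Materials and Method anticipates contrasts in how those assigned to "each regimen are affected with respect to functional attributes as well as in terms of constitutive skeletal muscle features (phenotype and gene signal patterns"). Sample size/Power describes Aim 2 as "a simplified comparison of those with gene expression below the median vs. those above the median". That wording implies pooled arms, although the plan does not say so outright. No by-arm version of the model is mentioned.

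**The concern.** If regimen changes the genes, and also changes function by routes other than the measured gene, it is a common cause of predictor and outcome. The plan itself describes such routes: the Background attributes the benefit of IMT to diaphragm strength, limb blood flow and the respiratory metaboreflex, while the biopsy is taken from the thigh. A slope fitted across all arms then combines two things: how gene change and functional change go together among patients on the same training, and how the arm averages line up.

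The direction cannot be predicted from the documents. Aim 2 does not assign aerobic training to either stimulation group, and the Background cites a view "with strength training much more likely to stimulate PGC-1 α than aerobic type exercise". The pooled slope could be nearly right, too small, too large, or present when no arm has any link.

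The trial's title promises to sort mechanisms of benefit, and this model is the one that relates the molecular change to the functional change. The randomised Aim 1 comparisons are not affected.

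**Working it through.** **The plan's own figure.** Sample size/Power gives 1.26 mL/kg/min as the detectable difference for Aim 2. At the stated 40 per group and 0.64 SD the difference is 0.64 x 2.2 = 1.41. The value 1.26 needs 48 per group: 2.80 x 2.2 x sqrt(2/48) = 1.26. That mismatch is a separate matter. What counts here is that the figure is for a two-group split with no regimen term.

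**Inputs from the documents**
- Table 5: aerobic 60, combined 30, IMT 60. Less 20% attrition: 48, 24, 48 (total 120; weights 0.4, 0.2, 0.4).
- SD of change in peak VO2: "we obtain a SD value of 2.2 for a 3-month intervention".
- Peak VO2 change (Sample size/Power): aerobic 0.6, combined 2.1, IMT 4.0. A second IMT trial in the Background gives less: "and also increased peak VO_2 (17.8 ± 1.2 versus" 15.4, so 17.8 - 15.4 = 2.4.

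**Assumptions, not in the documents**
- Gene change has SD 1 within each arm, and its mean shift differs by arm as shown below.
- The true within-arm slope is either 0 or 0.3 x 2.2 = 0.66 per SD of gene change (r = 0.3).
- Arm means for peak VO2 stay at the cited values.

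**Formula.** Pooled slope = (within-arm slope + between-arm covariance of gene shift and VO2 change) / (1 + between-arm variance of gene shift).

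*Aerobic and combined arms shift 0.5 SD more than IMT.* Their mean VO2 change is (48 x 0.6 + 24 x 2.1)/72 = 1.1. The variance is 0.6 x 0.4 x 0.5² = 0.06.
- IMT 4.0: covariance 0.24 x 0.5 x (1.1 - 4.0) = -0.348; slope (0.66 - 0.348)/1.06 = 0.29.
- IMT 2.4: covariance 0.24 x 0.5 x (1.1 - 2.4) = -0.156; slope (0.66 - 0.156)/1.06 = 0.48.

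*Only the combined arm shifts 0.5 SD, IMT 4.0.* The other two arms average 2.3. The covariance is 0.16 x 0.5 x (2.1 - 2.3) = -0.016; slope 0.644/1.04 = 0.62.

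*Shifts follow the VO2 order (0, 0.25, 0.5 SD).* The variance is 0.4 x 0.25² x 2 = 0.05.
- IMT 4.0: covariance 0.4 x 0.25 x (4.0 - 0.6) = 0.34; slope (0.66 + 0.34)/1.05 = 0.95.
- IMT 2.4: covariance 0.4 x 0.25 x (2.4 - 0.6) = 0.18; slope (0.66 + 0.18)/1.05 = 0.80.

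**Rejection rates without regimen** (20,000 simulated trials per scenario, ordinary least squares, two-sided 5%). False positives are for true slope 0; slope and power are for true slope 0.66.

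| Assumed gene shift | IMT gain | False positives | Slope | Power |
|---|---|---|---|---|
| Aerobic and combined +0.25 SD | 4.0 | 11% | 0.48 | 50% |
| | 2.4 | 7% | 0.57 | 78% |
| Aerobic and combined +0.5 SD | 4.0 | 27% | 0.29 | 22% |
| | 2.4 | 11% | 0.48 | 63% |
| Aerobic and combined +1.0 SD | 4.0 | 75% | -0.03 | 4% |
| | 2.4 | 25% | 0.28 | 29% |
| Combined only, +0.25 to +1.0 SD | 4.0 | 5% | 0.65 to 0.54 | 77% to 68% |
| | 2.4 | 5-7% | 0.65-0.68 | 90-92% |
| VO2 order, 0/0.25/0.5 SD | 4.0 | 27% | 0.95 | 98-99% |
| | 2.4 | 13% | 0.80 | 98-99% |

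If the regimens do not differ in VO2 change, false positives are 5%. With regimen in the model, every scenario gives 5-6% false positives, slope 0.66 and power 91-92%.

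**1RM.** The documents give no SD of change, so this is in SD units. If the aerobic and combined arms gain 0.5 or 1.0 SD more 1RM than IMT and shift genes 0.5 SD more, false positives are 10% or 21%. A true slope of 0.30 then reads (0.30 + 0.06)/1.06 = 0.34 or (0.30 + 0.12)/1.06 = 0.40.

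**The case against.** **The extreme rows are weakly anchored.** This stands. The Background reports the IMT trial behind the 4.0 figure as a 17% gain in peak VO2. A gain of 4.0 at 17% implies a baseline of 4.0/0.17 = 23.5, close to the pilot's control mean (23.4) and not its heart failure mean (15.4). Seventeen percent of 15.4 is 2.6, near the 2.4 above. At 2.6, with the aerobic and combined arms shifted 0.25, 0.5 or 1.0 SD, false positives are 7%, 12% and 32% and slopes are 0.56, 0.45 and 0.24. A 1.0 SD shift also exceeds the pilot's whole gap between heart failure and control, which is about 0.6 SD for FoxO3, FoxO1 and UBB (cross-sectional SDs, so only a rough guide). The rows with IMT 4.0 or a 1.0 SD shift should be read as outer bounds.

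**The confounder list may not be closed.** The eligibility and assessment sections name statins, other medications, sleep, diet and physical activity as factors to consider. None of these places names regimen, and General considerations ties the 10% rule to what is outlined for each analysis. One part of the document just before the statistics text was not available to this review.

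**Aim 2 does not rest on this slope alone.** Regimen is modelled directly against gene change and against function, and the plan says it will not lean on isolated significant results. That is true, but a shared regimen effect can distort several genes together, so looking at the overall pattern does not protect against it.

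**Adjustment has a price.** If regimen acts on function wholly through the measured gene, the pooled slope is unbiased (0.66) and has slightly more power: 93-96% against 91%. The adjusted slope is also observational, since it rests on variation between patients on the same training. Both points stand. They support reporting both slopes, not omitting the adjusted one.

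**Sample size.** Sample size/Power and Limitations say 210 patients, and four arms are mentioned in places; the working uses Table 5. The slope formula depends on the arm proportions, not the total.

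**Conclusion.** The concern holds. The gene-to-function model as written has no regimen term and no rule that could bring one in, while the plan expects regimen to move both sides of the regression. A significant slope could not then be read as a link between gene and function among patients on the same training.

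The size and sign are unknown in advance because they depend on gene shifts by arm, which are assumed here. With an IMT gain of 2.4 and shifts of 0.25 to 0.5 SD, false positives run from 5% to 13% and a true slope of 0.66 reads between 0.48 and 0.80. A gain of 4.0 or a 1.0 SD shift gives much larger distortion, up to 75% false positives when both apply. If only the combined arm shifts, there is little bias, though power falls when the IMT gain is 4.0. This is a change the plan should make, held with medium confidence as to how much it will matter in practice.

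**What to change.** Enter training regimen as a fixed categorical term in every Aim 2 gene-to-function model, for both peak VO2 and 1RM, and do not subject it to the 10% rule. Report the within-regimen slope as the Aim 2 result and the pooled slope beside it as description. As an optional sensitivity analysis, add training dose from the activity-monitor and TIRE adherence records already planned. Those data are too partial for the main model, because the monitor is worn one week a month where possible and TIRE covers the IMT arm only.

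The cost is two degrees of freedom for three arms and no new data. The slope then relies on within-regimen variation, and under full mediation it gives up the few points of power noted above. Where gene shifts follow the VO2 order, the pooled model rejects more often (98-99% against 91%), but with an inflated slope, so nothing of value is lost.

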The strength-aerobic combination has also been demonstrated to effectively modify inflammation. Conraads et al. (68) demonstrates decreased markers of inflammation, cytokines and cytokine receptors in HF patients after exercise training. They examined the effects of a 4 month training program (N=23) where the HF patients exercised 3 times per week for one hour. Training involved 30 minutes of resistive weight training and 20 minutes of cycling or jogging. Exercise training reduced circulating cytokines and improved peak VO_2 . Significant improvements were also seen in NYHA functional class, submaximal and maximal work rate, and work efficiency.

- **Inspiratory Muscle Training (IMT):** HF patients have also been demonstrated to have reduced inspiratory muscle strength and endurance which exacerbates dyspnea (69) and exercise intolerance. Inspiratory muscle strength correlates to VO_2 in HF and is an independent predictor of survival, i.e., comparable to peak VO_2 as a predictor of survival (70,71).

IMT has the potential to improve the respiratory muscle metaboreflex as well as many of pathophysiologic manifestations of HF. Quality of life, heart rate, respiratory rate, peak VO_2 , 6MWT distance, VE, the VE/VCO₂ slope and oxygen uptake efficiency slope (OUES), and recovery oxygen kinetics have all been shown to significantly improve after IMT (11-16) in HF patients.

Dall'Ago et al studied the benefits of IMT in 32 HF patients in a randomized, controlled 12 week trial. Maximal inspiratory pressure increased 115% in the IMT group with 17% improvement in peak VO_2 and 19% improvement in 6MWT distance (12). Even more compelling, Chiappa et al. (13) showed that IMT improved blood flow to resting and exercise limbs in the HF population. Specifically, a 4 week IMT regimen reduced calf vasoconstriction and improved forearm blood flow, i.e., systemic benefits were derived from the inspiratory training regimen as well as diaphragmatic hypertrophy. This account suggests IMT is analogous to strength training, such that high intensity IMT stimulates cell growth with peripheral adaptations.

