In summary, our proposal responds to the clinical challenge of treating HF, a disease that is already common and that will increase in prevalence as the population of older adults expands. HF-related decrements in physical function correspond to specific skeletal muscle gene expression patterns and there is compelling rationale that exercise training can improve function by inducing different molecular skeletal muscle signaling patterns. Using the excellent infrastructure and methodology we established in the course of our pilot work, we plan to implement and compare the effects of 4 different training regimens, delineating functional changes after training as well as skeletal muscle molecular signaling patterns underlying these differences.

PRELIMINARY DATA

1. Pilot Project

The pilot project *Ubiquitin Proteolysis and PGC-1 α in Skeletal Muscle in Heart Failure* closed enrollment on October 1, 2011. Analysis is ongoing, but multiple reports have already been generated that substantiate the premise for this investigation. Moreover, the body of work and productivity attest to [name] capacity to work effectively with Merit funding. This activity also corresponds to an evolution of methods and sophistication in the molecular assessments that are certain to enhance efficacy as our investigations accelerate and broaden.

The initial phase of work (before transcriptional data were available from muscle biopsies) was particularly oriented to functional assessments in relation to body composition in HF vs. controls. We also embarked on the novel assessment of CPX in terms of recovery dynamics after exercise.

A second phase of analysis (now underway) is focusing on gene expression patterns in relation to functional attributes and body composition. This work substantiates the hypotheses of the pilot investigation, i.e., that specific gene expression profiles underlie different performance attributes. These insights also support the rationale of the proposed trial. A third phase of work is anticipated shortly, i.e., integration of serologic markers for inflammation and metabolism to the assessments of genes, muscle function, and body composition, and to thereby expand the breadth and sophistication of our analyses.

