- *Regimen #1: Aerobic Training:* Aerobic endurance exercise entails rhythmic motion of large muscle groups in aerobic activities such as walking, jogging, and cycling, employing a general principle that exercise should exceed baseline capacities and thereby induce progressive physiological adaptations.

Initially, aerobic training intensity will be guided by the VAT delineated by CPX, which has been validated as an optimal training stimulus. The Borg scale (rate of perceived exertion index) from 6 to 20 will be used to help guide exercise from moderate to high training intensity (12 to 16) over the course of the trial. The aerobic exercise period will total 50 minutes (preceded and followed by warm-up and cool-down respectively); if the

patient cannot initially sustain exercise for this duration, shorter intervals of exercise will be used (e.g., exercise then rest then exercise using a 2/1 work to rest ratio with aims of 10 minute bouts of continuous exercise), that progressively elongate over weeks towards a 50 minute continuous exercise maximum

Walking is the preferred mode of aerobic exercise, using higher walking speed used to achieve greater intensity as needed. However, exercises utilizing other equipment that involve major muscle groups of the lower extremities (e.g. exercise bicycle) may be incorporated into the endurance training to supplement walking. Exercise will be monitored through the use of an activity monitor with accelerometer functions.

- *Training Regimen #3: Combined Aerobic-Strength Exercise Training:* The combined strength and aerobic regimen will be designed such that subjects begin exercise at a low intensity and then progress as tolerated. Strength training will focus on the major groups of muscles in the upper and lower extremities. The aerobic training will focus on increasing the subject's aerobic stamina.

Exercise sessions will last 50 minutes and start with a 5 minute low intensity warm up and end a 5 minute cool down. All subjects will progress towards 25 minutes of continuous aerobic exercise followed by 25 minutes of strength training. Strength training will consist of dynamic concentric and eccentric contractions of the upper and lower extremities using the same techniques as described above.

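### Aim 2 tests regimen against gene expression only through a two-way split whose sides are not assigned; the randomised arm should be the factor, with the split kept as a named contrast

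*Combined protocol and SAP*

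**What the plan says.** In the statistical section of the combined protocol and SAP, Aim 2 is "To assess gene expression and skeletal muscle perfusion in relation to the different training regimens". Two gene-expression analyses follow.

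- In the first, gene change is the predictor and function is the outcome: "Separate general linear models for each functional outcome will be performed with gene expression changes as the primary predictor". Training regimen is not a term in that model.
- In the second, "Treatment regimens will also be categorized as those with and without direct skeletal muscle stimulation". The resulting two-level factor then serves as the explanatory term, with change in gene expression as the outcome. The arms belonging to each category are not listed.

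A separate sentence covers perfusion and uses "aerobic and inspiratory training vs. strength-only training as a categorical predictor". Aim 1, by contrast, takes training regimen itself as the categorical predictor.

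Table 5 enrols three arms: aerobic 60 (35 Pittsburgh, 25 Boston), IMT 60 (35 and 25) and combined 30 (Pittsburgh only). The multi-site expansion text, Aim 1 and the Sample size/Power paragraph still refer to a strength arm or to four arms, and the last of these gives 210 patients.

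**The concern.** The background summary promises a comparison of regimens, "delineating functional changes after training as well as skeletal muscle molecular signaling patterns underlying these differences". A two-level variable cannot deliver that. Whichever side each arm is on, one level pools two regimens, so a positive result does not say which of them moved the gene.

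The side matters most for aerobic training, and the documents point both ways.

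- **Towards *with*:** the regimen description says "Aerobic endurance exercise entails rhythmic motion of large muscle groups in aerobic activities such as walking, jogging, and cycling", and the biopsied muscle is the vastus lateralis.
- **Towards *without*:** the perfusion contrast puts aerobic together with inspiratory training. The background on combined training also links the direct growth stimulus to the rationale for combining the two modes.

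The cited evidence does not settle it either. The background reports that aerobic training lowered FoxO3 and raised local IGF-1, gives inconsistent PGC-1α results, and mentions a view that strength work is the likelier PGC-1α stimulus. A placement that suits one Aim 2 gene may dilute another. Until the sides are fixed, the choice can be made after the gene data have been seen.

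**Working it through.** **Inputs.** Arm and site sizes are from Table 5. Attrition of 20%, two-sided 5% alpha, 80% power and 0.64 SD are from Sample size/Power. Completers are therefore 48 aerobic, 48 IMT and 24 combined. The documents give no gene-expression effect sizes, so I assume a combined effect *d*, an aerobic effect *f·d* with *f* from 0 to 1, and an IMT effect of 0.

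**1. The plan's own figure.** With 40 per group, SE = √(1/40 + 1/40) = 0.224 SD. The detectable difference is 0.634 SD by noncentral t and 0.626 SD by normal approximation, so the stated 0.64 reproduces (power at 0.64 is 80.7%). The Aim 2 power statement concerns a median split on gene expression with peak VO₂ as outcome. The with/without comparison has no stated power.

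**2. Effect kept by each placement.**

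- Aerobic in *without* (30 v 120): *d* − *f·d*·60/120 = *d*(1 − *f*/2).
- Aerobic in *with* (90 v 60): (30*d* + 60*f·d*)/90 = *d*(1 + 2*f*)/3.

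Power is at *d* = 0.64 SD with 48/48/24 completers. The last column is the three-arm test on 2 df.

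| *f* | Kept, aerobic in *without* | Kept, aerobic in *with* | Power, *without* | Power, *with* | Power, three-arm |
|---|---|---|---|---|---|
| 0 | 100% | 33% | 79.4% | 20.5% | 69.8% |
| 0.5 | 75% | 67% | 55.0% | 62.2% | 63.5% |
| 1 | 50% | 100% | 28.5% | 92.6% | 86.9% |

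The two-thirds loss depends on the 2:2:1 allocation. With three equal arms (210/3 = 70, an assumption) the shares are 1 − *f*/2 and (1 + *f*)/2, and the worst loss is one half either way.

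**3. Price of modelling the arms.** At these sample sizes the detectable difference is about 2.825 × SE.

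| Comparison | SE (SD units) | Detectable |
|---|---|---|
| Pooled, aerobic in *with* (72 v 48) | √(1/72 + 1/48) = 0.186 | 0.53 SD |
| Pooled, aerobic in *without* (24 v 96) | √(1/24 + 1/96) = 0.228 | 0.645 SD |
| Average of aerobic and combined v IMT, three-level model | √(¼·1/48 + ¼·1/24 + 1/48) = 0.191 | 0.54 SD |
| Aerobic v IMT | √(1/48 + 1/48) = 0.204 | 0.58 SD |
| Combined v aerobic, or v IMT | √(1/24 + 1/48) = 0.250 | 0.71 SD |

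With Bonferroni for three contrasts, the last row becomes 0.82 to 0.83 SD, depending on the error degrees of freedom.

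**4. Adding site.** Completers are 28/28/24 in Pittsburgh and 20/20/0 in Boston.

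- Combined v aerobic (or IMT): variance 1/24 + 1/56 + 1/96 = 0.0699, SE 0.264, detectable 0.75 SD.
- Average contrast: variance 0.75²·(2/48) + 0.5²·(1/24 + 1/56) = 0.0383, SE 0.196, detectable 0.55 SD.

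**The case against.** There is a fair case for leaving the split alone.

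- **Pooling looks deliberate.** Sample size/Power says that combining training groups allows smaller differences to be detected, and the general considerations show concern about type I error. A correctly placed split does beat the 2-df test (79.4% v 69.8%, and 92.6% v 86.9%). This stands, and it is why a pooled contrast should be kept. It does not justify leaving the sides unnamed.
- **The meaning may be clear enough.** With a thigh biopsy, IMT against the rest is the natural reading, and the perfusion contrast concerns a different outcome. This largely stands: the two placements are not equally likely. But the text does not state it, and the combined-training background pulls the other way.
- **The split is not all of Aim 2.** The gene-to-function models do not use it, and the plan says isolated associations will not be unduly weighted. So the claim that the whole mechanistic conclusion hangs on one arm is not supported.
- **Text may be missing.** Material just before the statistical section was not available. A definition there cannot be excluded.

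A reader might infer that the analysis will lose half to two thirds of its effect. The documents do not support that. Such a loss needs aerobic on the wrong side, an all-or-none aerobic effect, and no IMT effect at all. The background also says "This account suggests IMT is analogous to strength training", so inert IMT is a working assumption for the dilution figures and not a finding.

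**Conclusion.** The point holds in a limited form. The only regimen-to-gene model in the available text does not answer the regimen question that Aim 2 sets, and the variable it uses is not defined there.

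The dilution from misplacing aerobic ranges from nothing to one half (aerobic in *without*, fully active) or two thirds (aerobic in *with*, inert). At a half-strength aerobic effect it is 25% or 33% respectively. These figures rest on the 60/60/30 allocation and inert IMT.

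The firmer ground does not depend on those assumptions: either split hides which regimen acts, and the placement can still be chosen after the data are seen. The remedy costs almost nothing on the pooled question (0.54 v 0.53 SD). It should be made before gene data are examined.

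**What to change.** In the Aim 2 gene-change models:

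1. Use the randomised arm as the categorical factor, as in Aim 1, and include site as a covariate, because combined training is enrolled only in Pittsburgh.
2. Keep the with/without question as one pre-specified linear contrast in that model, naming each arm's side before gene data are seen. The average of aerobic and combined against IMT is one example.
3. Report the pairwise arm contrasts as secondary. They are needed because the averaged contrast still estimates only *d*/2 if aerobic is inert.
4. Reconcile the four-arm and strength-only wording in the multi-site expansion text, Aims 1 and 2, and Sample size/Power with Table 5. Any arm that remains needs a stated side.

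The change is to SAP wording, with the same data and the same general linear model. The plan should state the downside: contrasts involving combined training detect only about 0.71 SD before multiplicity and site adjustment (about 0.75 SD with site), and there are more tests per gene. The change does not remove plate differences if the rtPCR runs are batched by exercise arm, as the laboratory section proposes; that needs separate attention.
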